2.2 Analysis sets

Full Analysis Set

The Full Analysis Set (FAS) comprises all enrolled participants.

Enrollment will take place at the time when all eligibility requirements are confirmed.

Efficacy Analysis Set

The Efficacy Analysis Set (EFF) comprises all enrolled participants who were administered with [⁶⁸Ga]Ga-DOTA-TATE. Patients with confirmed/suspected NENs must have both results of [⁶⁸Ga]Ga-DOTA-TATE PET/CT imaging and CIM. HVs must have result of [⁶⁸Ga]Ga-DOTA-TATE PET/CT imaging. If at least 1 central reader cannot judge results for all CIM or

[⁶⁸Ga]Ga-DOTA-TATE PET/CT imaging due to imaging quality, the results are considered as "Not evaluable". Those participants will be excluded from the EFF.

A result considered "Not evaluable" if the following scenarios happened:

- There is no subject-level result due to poor imaging quality or insufficient coverage.
- There is no accurate subject-level result because one or more region-level result are not readable and all other region-level result are negative.

Safety Set

The Safety Set comprises all participants who received any dose of [⁶⁸Ga]Ga-DOTA-TATE.

Pharmacokinetic Analysis Set

The Pharmacokinetic Analysis Set (PAS) includes all participants who provided at least one evaluable PK concentration. A profile is considered evaluable if all of the following conditions are satisfied:

- Participant received the study drug
- Participant provided at least one primary PK parameter

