9.3.7 Supplementary analysis

If the primary endpoints of subject-level sensitivity and specificity are met, following supplementary analyses will be conducted.

- TP, FP, FN, TN, sensitivity, specificity and corresponded exact 95% CI will be shown for each 3 central readers respectively.
- If there are participants with not evaluable [⁶⁸Ga]Ga-DOTA-TATE PET/CT imaging, those participants' results will be assumed all positive or all negative respectively and each analysis will be performed for primary endpoints.
- The subgroup analyses using descriptive statistics and 95% CI to assess the homogeneity of the diagnostic performance of [⁶⁸Ga]Ga-DOTA-TATE PET/CT imaging across demographic and baseline disease characteristics will also be performed. Important subgroups will be specified in the SAP.

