1.2.1 Primary estimand(s)

The primary clinical question of interest is: What is the probability that [⁶⁸Ga]Ga-DOTA-TATE PET/CT imaging truly detects tumor lesion(s) in subject-level for NENs using CIM (including [¹¹¹In]In-Pentetreotide SPECT/CT and High Resolution CT with contrast (or MRI if CT with contrast is medically contraindicated) as standard of truth).

The justification for the primary estimand is that it will capture the diagnostic performance of [⁶⁸Ga]Ga-DOTA-TATE PET/CT imaging in detecting tumor lesion(s) in NENs subjects. For this reason, participants with confirmed or suspected NENs will be investigated with CIM obtained on or before screening phase (HVs will be categorized as CIM negative without performing CIM) and confirmed or suspected NENs and HVs will be investigated with [⁶⁸Ga]Ga-DOTA-TATE PET/CT imaging on treatment phase, and the results of [⁶⁸Ga]Ga-DOTA-TATE PET/CT imaging will be compared against the results of CIM as standard of truth. The primary estimands are described by the following attributes:

Primary estimand 1:

1. Population: Patients who show at least one lesion based on CIM by central read, received [⁶⁸Ga]Ga-DOTA-TATE, completed a PET/CT scan and had a central read of the [⁶⁸Ga]Ga-DOTA-TATE PET/CT imaging.
2. Variable: The result of [⁶⁸Ga]Ga-DOTA-TATE PET/CT imaging (positive (i.e., showing at least one lesion) or negative (i.e., not showing any lesion)). In the population above, a participant with positive on [⁶⁸Ga]Ga-DOTA-TATE PET/CT imaging corresponds to True positive (TP) and a participant with negative on [⁶⁸Ga]Ga-DOTA-TATE PET/CT imaging corresponds to False negative (FN).
3. Treatment of interest: [⁶⁸Ga]Ga-DOTA-TATE injected as a single intravenous dose of 2 MBq/kg (0.054 mCi/kg) of body weight up to a maximum total dose of 200 MBq (5.4 mCi).
4. Intercurrent events: None
5. Summary measure: Estimate of proportion of participants who test positive on [⁶⁸Ga]Ga-DOTA-TATE PET/CT imaging (TP) among those who are CIM positive (TP+FN according to [⁶⁸Ga]Ga-DOTA-TATE PET/CT imaging) (subject-level sensitivity), along with 95% confidence interval.

Primary estimand 2:

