2.3 Patient disposition, demographics and other baseline characteristics

2.3.1 Patient disposition

Screen phase disposition will be summarized for all screened participants. The number (%) of screened/ enrolled/ not enrolled participants and the primary reason for not completing screen phase will be summarized. For rescreened participants, only status of rescreening will be included in the summaries.

Information of informed consent from each screened participant will be listed.

For enrolled participants in the FAS, all disposition information will be summarized and listed.

Protocol deviations

Protocol deviations will be summarized for the FAS.

The number (%) of participants with any reportable protocol deviation will be tabulated by deviation category (as specified in the Edit Check Specifications).

All protocol deviations will be listed.

Analysis sets

The number (%) of patients in each analysis set (defined in [Section 2.2](#)) will be summarized for the FAS.

Participants included in each analysis set will be listed.

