2.5.2 Statistical hypothesis, model, and method of analysis

To address the co-primary objectives, following analyses will be conducted.

Subject-level sensitivity and its 95% exact confidence interval (CI) will be calculated based on the binomial distribution. The lower bound of the 95% exact CI for subject-level sensitivity should be greater than 0.7 to attain the first co-primary objective.

Subject-level specificity and its 95% exact CI will be calculated based on the binomial distribution. The lower bound of the 95% exact CI for subject-level specificity should be greater than 0.6 to attain the second co-primary objective.

Listing for central imaging assessments will be provided for the FAS.

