2.5.6 Supplementary analyses

If the primary endpoints of subject-level sensitivity and specificity are met, following supplementary analyses will be conducted.

- TP, FP, FN, TN, sensitivity, specificity and corresponding exact 95% CIs will be shown for each of the 3 central readers.
- If there are participants who are excluded from the EFF, those participants' results will be assumed all positive or all negative respectively and each analysis will be performed for primary endpoints. Assumption of handling as all negative will be conservative for sensitivity and assumption of handling as all positive will be conservative for specificity.
- If there are participants with readable but not optimal [⁶⁸Ga]Ga-DOTA-TATE PET/CT imaging, analysis excluding those participants will be repeated for primary endpoints. If at least one reader reports readable but not optimal, then the imaging of the participant will be considered readable but not optimal.
- The subgroup analyses estimating subject-level sensitivity or specificity with corresponding exact 95% CIs will be performed. Subgroups of interest are specified in [Section 2.2.1](#).

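### SAP 2.6.4 rules out missing region-level data that the EFF rule allows, and the analysis that bounds EFF exclusions is skipped unless both co-primary endpoints are met

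*SAP*

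**What the plan says.** **EFF membership.** Under SAP 2.2 one reader is enough to remove a participant: "If at least 1 central reader cannot judge results for all CIM or" the PET/CT images because of image quality, the result is not evaluable and the participant leaves the EFF. The SAP names two such scenarios. The second is: "There is no accurate subject-level result because one or more region-level result are not readable and all other region-level result are negative". SAP 1.2.1 defines the PET result as "positive (i.e., showing at least one lesion) or negative (i.e., not showing any lesion").

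**Missing data.** SAP 2.6.4 states that neither the subject-level secondary endpoints nor the five region-level measures (sensitivity, specificity, PPV, NPV, accuracy) can have missing data within the EFF.

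**The bounding analysis.** SAP 2.5.6 and Protocol 9.3.7 open with the same condition: "If the primary endpoints of subject-level sensitivity and specificity are met, following supplementary analyses will be conducted". One of these analyses sets excluded participants to all positive, then all negative. The Protocol's version begins "If there are participants with not evaluable" PET/CT imaging; the SAP's begins "If there are participants who are excluded from the EFF". SAP Section 4 lists two other changes to the protocol analyses but not this one. SAP 2.5.5 plans no sensitivity analysis.

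**Outputs without the condition.** SAP 2.3.1 tabulates the number in each analysis set and adds: "Participants included in each analysis set will be listed". SAP 2.5.2 adds: "Listing for central imaging assessments will be provided for the FAS".

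**The concern.** Four things follow from reading these sections together.

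- **(a)** The second scenario removes a participant with an unreadable region only if every other region is negative. Those with a lesion elsewhere remain, so the region-level tables can have gaps that SAP 2.6.4 says do not exist. A programmer could count such a region as negative or leave it out, and the reader would not know which.
- **(b)** Whether a participant with an unreadable region counts in the primary analysis depends partly on what PET showed in the other regions.
- **(c)** The analysis that would show how much the exclusions matter is withheld in every outcome except a double success. SAP 2.5.2 defines attainment of each co-primary objective separately, so sensitivity could be reported as attained beside a failed specificity with no bound on its exclusions.
- **(d)** The bounded set differs between Protocol and SAP, and the difference is unrecorded. The wider SAP set takes in any patient without an evaluable conventional imaging (CIM) result, who belongs to neither denominator.

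**Working it through.** **1. The plan's own figures.** Inputs from SAP Section 3: one-sided 2.5%, exact binomial; sensitivity 0.90 against 0.70 with N = 47; specificity 0.90 against 0.60 with N = 23. The smallest counts whose exact lower bound clears the threshold are 40/47 (0.717; 39/47 gives 0.692) and 19/23 (0.612; 18/23 gives 0.563). Power is P(X ≥ 40 | 47, 0.90) = 0.907 and P(Y ≥ 19 | 23, 0.90) = 0.927, matching the 90.7% and 92.7% in SAP Table 3-1.

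**2. What SAP 2.2 does with an unreadable region.**

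| Other regions | Subject-level result | In EFF? | Result for the unreadable region |
|---|---|---|---|
| All negative | Not evaluable | No | Not needed |
| At least one lesion | Positive (SAP 1.2.1) | Yes, by implication | Missing, no rule |

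The second row contradicts SAP 2.6.4. As an illustration with assumed counts, take a region with 20 readable CIM-positive results, 18 of them PET positive, and two more unreadable on PET. Sensitivity is 18/20 = 90.0% if the two are left out, 18/22 = 81.8% if counted negative and 20/22 = 90.9% if counted positive.

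**3. Size of the selection.** The documents give no unreadable rate, so these are assumptions: a share u of participants has an unreadable region regardless of the result; a share k of the PET-positive ones among them shows a lesion elsewhere and is kept; PET-negative ones are dropped; PET is treated as one combined read. For true sensitivity s,

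EFF sensitivity = s(1 − u + uk) / [s(1 − u + uk) + (1 − s)(1 − u)].

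| u | k | s = 0.90 | s = 0.70 |
|---|---|---|---|
| 2% | 1 | 0.902 | 0.704 |
| 5% | 1 | 0.905 | 0.711 |
| 10% | 0.8 | 0.907 | 0.718 |
| 10% | 1 | 0.90/(0.90 + 0.09) = 0.909 | 0.70/(0.70 + 0.27) = 0.722 |

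With k = 0 (no lesion visible in the readable regions) nothing shifts. Specificity moves the other way. At u = 10% and k = 1, a true 0.90 becomes 0.81/(0.81 + 0.10) = 0.890, and 0.60 becomes 0.54/(0.54 + 0.40) = 0.574. It too is unchanged at k = 0.

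If unreadability is related to the result, the direction can reverse. At true sensitivity 0.70, take 15% unreadable among PET positives, half of them still showing a lesion, and 5% unreadable among PET negatives. EFF sensitivity is then 0.70 × 0.925 / (0.70 × 0.925 + 0.30 × 0.95) = 0.6475/0.9325 = 0.694.

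**4. What the condition can leave unbounded.** Suppose sensitivity is 40/47 and specificity is missed. Counting one excluded CIM-positive participant as negative gives 40/48, lower bound 0.698, below 0.70. At 41/47 two such participants still leave a pass (41/49, 0.703) and three do not (41/50, 0.686). With a 47/23 split, true values 0.90/0.90 and independent endpoints, P(X = 40) = 0.0930 and P(specificity missed) = 1 − 0.9269 = 0.0731. The product is 0.0068, about 0.7%, before any exclusion is required.

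**5. Scope of the bound.** Protocol 9.3.7 covers not-evaluable PET. SAP 2.5.6 covers everyone outside the EFF, which adds participants not dosed, not scanned, or without an evaluable CIM. Both estimands in SAP 1.2.1 require dosing, a completed scan and a central PET read, so imputing results for the undosed or unscanned answers a different question.

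**The case against.** The strongest reply is that the plan already protects the claim that matters. A double success triggers the bound, so no declared overall success escapes it. The condition is prespecified in both documents. In other outcomes the analysis-set counts and the listing of central reads for all enrolled participants would let a reader rebuild a bound. All of that stands, and it keeps the point minor. What remains is that rebuilding a bound from listings is not a planned estimate, and that the conflict with SAP 2.6.4 is independent of the condition.

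Three stronger readings are tempting, and the documents do not support them.

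- A reader might take the chance that the condition fails as the size of the harm: 1 − 0.9072 × 0.9269 = 15.9% at design values. That is only the chance of missing a co-primary, computed with no exclusions, in which case there is nothing to bound.
- A reader might infer that the EFF rule inflates false success on sensitivity. In the model of step 3 the chance of reaching 40/47 at a true 0.70 rises from 0.014 to 0.020 at 5% unreadable and 0.029 at 10% (k = 1), passing the nominal 0.025 only at the higher rate. No rate is documented, the direction can reverse, and overall success also needs specificity, which moves the other way in the same model.
- A reader might infer that many patients lack a CIM class. Protocol 8.1.1 has the central CIM result confirmed at registration, so they should be few.

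Retention of a participant with a lesion elsewhere is inferred from the wording of SAP 2.2, not stated. Region reading rules may also sit in the Imaging Manual, which is not among the documents. Even so, SAP 2.6.4 needs a rule or a reference to one.

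**Conclusion.** The point holds and is minor. The firmest part is that the SAP 2.6.4 statement is not true of region-level endpoints under the SAP 2.2 rule, and no handling is given; these endpoints are secondary and descriptive. EFF membership does depend partly on the PET reading. If unreadability is unrelated to the result, the shift at an assumed 10% is at most about 0.01 for a true sensitivity of 0.90 and about 0.02 for 0.70, with specificity slightly lower, or no shift if the readable regions show no lesion. The direction is conditional and the actual rate is unknown. The condition on the bound does not conceal an inflated double success; it leaves half-met and failed results with counts and listings only. The widening from Protocol 9.3.7 to SAP 2.5.6 is an unrecorded departure.

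**What to change.** 1. **SAP 2.6.4.** Limit the statement that missing data cannot occur to the subject-level endpoints. Leave an unreadable region out of that region's denominator, and report the number of such regions with best- and worst-case bounds.
2. **SAP 2.5.6.** Run the all-positive/all-negative analysis whether or not the co-primary endpoints are met. Apply it to participants who were dosed and scanned, whose PET read is not evaluable, and who are healthy volunteers or have an evaluable CIM result. Report the other exclusions (undosed, no scan, CIM not evaluable) as counts by reason. Describe any direction of bias only conditionally.
3. **SAP Section 4.** Record both departures from Protocol 9.3.7: the condition removed and the bounded set redefined.

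The EFF definition, the success rule and the power stay as they are. The cost is SAP wording and a few extra tables, with no extra participants or reads. The downside for the sponsor is that a supporting figure may be less favourable.

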2.2.1 Subgroup of interest

Subgroup analyses will be conducted when the co-primary objectives of subject-level sensitivity and specificity are met.

The objective of the efficacy subgroup analysis is to demonstrate homogeneity of diagnostic performance of [⁶⁸Ga]Ga-DOTA-TATE PET/CT in the following subgroups.

For CIM positive population,

- NEN classification (NET, NEC, MiNEN, Other NEN)*
- NET grading (NET G1, NET G2, NET G3 (GEP-NET patients only))
- Functionality (Functional_All/ Carcinoid/ Gastrinoma/ Glucagonoma/ Insulinoma/ VIPoma/ Other, Non-functional)**
- Primary site of cancer***

* For NET and NEC, results will be presented regardless of the number of patients within each category. For MiNEN and Other NEN, only subgroup category results including 5 or more patients will be presented.

** Only subgroup category results including 5 or more patients will be presented.

*** Results of each category including 5 or more patients will be presented.

For CIM negative population,

- Population (patients, HV)****

**** Analysis will be conducted only if 5 or more patients are included.

2.3 Patient disposition, demographics and other baseline characteristics

2.3.1 Patient disposition

Screen phase disposition will be summarized for all screened participants. The number (%) of screened/ enrolled/ not enrolled participants and the primary reason for not completing screen phase will be summarized. For rescreened participants, only status of rescreening will be included in the summaries.

Information of informed consent from each screened participant will be listed.

For enrolled participants in the FAS, all disposition information will be summarized and listed.

Protocol deviations

Protocol deviations will be summarized for the FAS.

The number (%) of participants with any reportable protocol deviation will be tabulated by deviation category (as specified in the Edit Check Specifications).

All protocol deviations will be listed.

Analysis sets

The number (%) of patients in each analysis set (defined in [Section 2.2](#)) will be summarized for the FAS.

Participants included in each analysis set will be listed.

- For participants with primary onset: (the date of study informed consent – the date of initial diagnosis of NEN +1)/ 30.4375,
- For participants with relapse/progression*: (the date of study informed consent – the date of most recent relapse/progression of NEN +1)/ 30.4375.

* This includes participants who have both values of the date of initial diagnosis and the date of most recent relapse/progression.

Medical history

Medical history and current medical conditions will be summarized and listed. The summaries will be presented by primary system organ class (SOC) and preferred term (PT). Medical history and current medical conditions will be coded using the Medical Dictionary for Regulatory Activities (MedDRA) terminology. The MedDRA version used for reporting will be specified in the CSR and as a footnote in the applicable tables/listing.

2.4 Treatments (study treatment, rescue medication, concomitant therapies, compliance)

2.4.1 Study treatment / compliance

The actual received [⁶⁸Ga]Ga-DOTA-TATE dose (MBq), [⁶⁸Ga]Ga-DOTA-TATE dose per 1 kg (MBq/kg) and time interval (minutes) from injection of [⁶⁸Ga]Ga-DOTA-TATE to PET/CT acquisition start will be summarized by descriptive statistics using the Safety Set.

All dose administration records will be listed.

2.4.2 Prior, concomitant and post therapies

Prior anti-cancer therapy

Prior anti-cancer therapy analyses will be performed for the FAS and the EFF.

The number (%) of participants who received any prior anti-neoplastic medications, prior anti-neoplastic radiotherapy and prior anti-neoplastic surgery will be summarized.

Prior anti-neoplastic medications will be summarized by total number of regimens and setting by lowest ATC class and preferred term (PT).

Prior anti-neoplastic radiotherapies will be summarized by setting.

Prior anti-neoplastic surgeries will be summarized by type of surgery and presence of residual disease.

Separate listings will be produced for prior anti-neoplastic medications, radiotherapy, and surgery. Anti-neoplastic medications will be coded using the WHO Drug Dictionary (WHO-DD); anti-neoplastic surgery will be coded using MedDRA. Details regarding WHO-DD and MedDRA version will be included in the footnote in the tables/listings.

Concomitant medications, non-drug therapies and procedures

Concomitant medications analyses including non-drug therapies and procedures will be performed for the Safety Set.

Concomitant medications, non-drug therapies and procedures starts on or after the day of dosing of investigational drug but not more than 8 days after dosing of investigational drug (i.e. Day 1 – Day 9) or starts prior to and continues after the start of study treatment.

Only medications, non-drug therapies and procedures collected in the eCRF 'Prior or Concomitant Medications' and 'Prior or Concomitant Non-drug therapies and Procedures' will be included in concomitant medications, non-drug therapies and procedures; those collected in

the eCRF 'Prior Anntineoplastic Medications', 'Prior Antineoplastic Radiotherapies', and 'Prior Antineoplstic Surgeries' will not be included.

Concomitant medications will be coded using the WHO-DD and summarized by lowest ATC class and PT. Non-drug therapies and procedure will be coded using MedDRA and summarized by SOC and PT. Details regarding WHO-DD and MedDRA version will be included in the footnote in the tables/listings.

The listing includes all prior and concomitant medications, non-drug therapies and procedures will be provided. Any concomitant therapies starting and ending prior to the start of study treatment or starting 9 days after dosing of investigational drug (i.e. start from Day 10) will be flagged in the listing.

2.5 Analysis supporting primary objectives

All analyses supporting primary objectives will be performed for the EFF unless otherwise specified.

2.5.1 Primary endpoint(s)

The co-primary endpoints of the study are subject-level sensitivity and specificity.

Subject-level sensitivity

Subject-level sensitivity is defined as the proportion of $[^{68}\text{Ga}]\text{Ga}\text{-DOTA-TATE}$ PET/CT imaging positive participants (i.e. TP participants) among CIM positive participants (i.e. TP or FN participants).

Subject-level specificity

Subject-level specificity is defined as the proportion of $[^{68}\text{Ga}]\text{Ga}\text{-DOTA-TATE}$ PET/CT imaging negative participants (i.e. TN participants) among CIM negative participants (i.e. TN or FP participants).

Table 2-2 Sensitivity and Specificity

		Conventional Imaging (CIM)	
		Positive	Negative
$[^{68}\text{Ga}]\text{Ga}\text{-DOTA-TATE}$ PET/CT imaging	Positive	True Positive (TP)	False Positive (FP)
	Negative	False Negative (FN)	True Negative (TN)
Sensitivity: TP / (TP + FN), Specificity: TN / (TN + FP)			

Where TP, FP, TN, FN participants are defined as follows:

- TP participants are those who show at least one lesion based on both $[^{68}\text{Ga}]\text{Ga}\text{-DOTA-TATE}$ PET/CT imaging and CIM by central read.
- FP participants are those who show at least one lesion based on $[^{68}\text{Ga}]\text{Ga}\text{-DOTA-TATE}$ PET/CT imaging but do not show any lesion based on CIM by central read.
- TN participants are those who do not show any lesion based on both $[^{68}\text{Ga}]\text{Ga}\text{-DOTA-TATE}$ PET/CT imaging and CIM by central read.

- FN participants are those who do not show any lesion based on [⁶⁸Ga]Ga-DOTA-TATE PET/CT imaging but show at least one lesion based on CIM by central read.

